9.3.2 Analysis of the secondary efficacy endpoints

The secondary efficacy variables supporting the primary efficacy variable are listed below, and will be included in the multiplicity adjustment:

1. Proportion of study participants who achieve HiSCR₇₅ at Week 16. A similar analysis to the primary responder analysis will be performed.
 - a. bimekizumab [REDACTED] vs placebo
 - b. bimekizumab [REDACTED] vs placebo
2. Proportion of study participants who experience at least 1 flare by Week 16, with flare defined as a $\geq 25\%$ increase in AN count with an absolute increase in AN count of ≥ 2 relative to Baseline. A similar analysis to the primary responder analysis will be performed.
 - a. bimekizumab [REDACTED] vs placebo

-
- b. bimekizumab [REDACTED] vs placebo
3. Absolute change from Baseline in DLQI Total Score at Week 16. Analysis will be based on an analysis of covariance (ANCOVA) with treatment and stratification variables as fixed effects and the Baseline values as covariate.
- a. bimekizumab [REDACTED] vs placebo
- b. bimekizumab [REDACTED] vs placebo
4. Absolute change from Baseline in Skin Pain Score at Week 16, as assessed by the “worst pain” item (11-point numeric rating scale) in the HSSDD. Analysis will be based on an ANCOVA with treatment and stratification variables as fixed effects and the Baseline values as covariate.
- a. bimekizumab [REDACTED] vs placebo
- b. bimekizumab [REDACTED] vs placebo
5. Pain response (defined as a decrease from Baseline in HSSDD weekly worst skin pain score at or beyond the threshold for clinically meaningful change) at Week 16. A similar analysis to the primary responder analysis will be performed.
- a. bimekizumab [REDACTED] vs placebo
- b. bimekizumab [REDACTED] vs placebo

[figure not shown]
To control the overall type I error rate at 0.05 for the multiple comparisons in the primary and secondary efficacy variables, a closed testing procedure under a parallel gatekeeping framework will be applied (Sun, 2018).

Under this framework, each bimekizumab dose of [REDACTED] and [REDACTED] will be compared to placebo in the first instance at a familywise error rate of 0.025 ($\alpha/2$). Simultaneously within each dose, closed testing for the primary and secondary efficacy endpoints will be performed as follows:

1. Step 1: Test $HiSCR_{50}$ at significance level 0.025.
2. Steps 2 to 6 – If Step 1 is significant at 0.025 then test each secondary endpoint sequentially in the order shown below, moving to the next step only if significance achieved at 0.025.
3. In the event that Step 6 is significant at 0.025 for a given dose, then Steps 1 to 6 will be repeated for the other dose using a significance level of 0.05.

A schematic of the procedure is shown in [Figure 9-1](#).

Figure 9-1: Closed Testing Procedure

AN=abscess and inflammatory nodule; CFB=change from Baseline; DLQI=Dermatology Life Quality Index; HiSCR₅₀=a 50% reduction in the total AN count with no increase from Baseline in abscess or draining tunnel count; HiSCR₇₅=a 75% reduction in the total AN count with no increase from Baseline in abscess or draining tunnel count; HS=hidradenitis Suppurativa; [REDACTED]

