
Evaluate the efficacy of bimekizumab on abscesses, nodules, and draining tunnels at various timepoints in study participants with moderate to severe HS
	
 • Change and percentage change from Baseline in lesion counts (abscess count, inflammatory nodule count, AN count, and draining tunnel count) • AN count of 0, 1, or 2 • AN₂₅, AN₅₀, AN₇₅, AN₉₀, AN₁₀₀ • Flare (defined as a $\geq 25\%$ increase in AN count with an absolute increase in AN count of ≥ 2 relative to Week 16) by Week 48 • Time to flare from Weeks 0 to 16 • Time to flare from Week 16 to 48

Evaluate the efficacy of bimekizumab on patient-reported outcome measures at various timepoints in study participants with moderate to severe HS
	
 • Absolute and percentage change (worst and average pain) from Baseline in HS Skin Pain score (11-point numeric rating scale) • Pain response (defined as a decrease from Baseline in HSSDD weekly worst skin pain score at or beyond the threshold for clinically meaningful change) • Pain response (defined as a decrease from Baseline in HSSQ weekly worst skin pain score at or beyond the threshold for clinically meaningful change) • Pain response (at least a 30% reduction and at least a 1-unit reduction from Baseline in HSSDD weekly worst skin pain score [11-point numeric rating scale]) among study participants with a score of ≥ 3 at Baseline • Pain response (at least a 30% reduction and at least a 1-unit reduction from Baseline in HSSDD weekly average skin pain score [11-point numeric rating scale]) among study participants with a score of ≥ 3 at Baseline • Pain response (at least a 30% reduction and at least a 1-unit reduction from Baseline in HS Skin Pain score [11-point numeric rating scale]) assessed by the HSSQ among study participants with a score of ≥ 3 at Baseline • Absolute change from Baseline in DLQI Total Score • DLQI Total Score of 0 or 1

Objectives	Endpoints

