9.1.2 Randomized Set

The Randomized Set (RS) will consist of all randomized study participants.

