9.3 Planned efficacy/outcome analyses

9.3.1 Analysis of the primary efficacy endpoint

The primary objective of this randomized, double-blind, placebo-controlled, multicenter, pivotal study in study participants with moderate to severe HS is to compare the efficacy of bimekizumab [REDACTED] and bimekizumab [REDACTED] with placebo at Week 16. For the purposes of Week 16 analyses, the bimekizumab treatment arms of [REDACTED] and bimekizumab [REDACTED] treatment groups will be pooled.

The primary and secondary efficacy analyses will be performed based on the RS.

The primary endpoint is the HiSCR₅₀ response at Week 16. The primary efficacy analysis will evaluate the composite estimand in the RS. The composite estimand combines the clinically meaningful improvement from Baseline based on the HiSCR₅₀ response and early receipt of

systemic antibiotic rescue medication, or discontinuation of IMP due to an AE or lack of efficacy.

The following 4 attributes describe the estimand that will be used to define the treatment effect of interest for the primary efficacy analysis:

1. Population=Study participants meeting the protocol-specified inclusion/exclusion criteria.
2. Study participant-level outcome=HiSCR₅₀ at Week 16.
3. Intercurrent event handling=An intercurrent event is defined as receipt of systemic antibiotic rescue medication or discontinuation of study treatment due to an AE or lack of efficacy prior to Week 16. A composite strategy will be implemented in which a positive clinical outcome is defined as achieving HiSCR₅₀ at Week 16 and not receiving systemic antibiotic rescue medication, and not discontinuing study treatment due to an AE or lack of efficacy through Week 16. Any missing data at Week 16 that are not preceded by an intercurrent event will be imputed using multiple imputation.
4. Population-level summary measure=conditional odds ratio comparing bimekizumab to placebo adjusted for stratification factors used in the randomization.

As a sensitivity analysis, any missing data at Week 16 that are not preceded by an intercurrent event (ie, receipt of systemic antibiotic rescue medication, or discontinuation of IMP due to an AE or lack of efficacy) will be imputed as non-response.

The statistical hypothesis for the HiSCR₅₀ response at Week 16 is that the conditional odds ratio for the HiSCR₅₀ response in the bimekizumab treatment group relative to the placebo group is equal to 1.

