After randomization for this study was complete, an additional endpoint to assess Worst Pain response was included in the sequential testing procedure. This additional endpoint is defined as HSSDD weekly worst skin pain score at or beyond the threshold for clinically meaningful change at Week 16. Note that the power calculations reported in Table 9-1 for this endpoint are based on the sample size that was initially driven by the Worst Pain CFB endpoint as described above. With a 2-sided significance level of 0.025, the sample size of 104:52 in the subset of participants reporting Baseline HSSDD worst skin pain score at or beyond the threshold for clinically meaningful change (ie, Baseline HSSDD \geq threshold value) provides 53% power for detecting a statistically significant difference between bimekizumab [REDACTED] and placebo in the proportion of Worst Pain responders.

Note that the power at the 0.025 level of significance associated with this endpoint for the comparison between bimekizumab [REDACTED] and placebo is 95%. The [REDACTED] comparison of Worst Pain response vs placebo against the 0.05 level of significance is therefore likely, and the power at this significance level is 65%. Given the strength of the power for the bimekizumab [REDACTED] arm vs placebo across endpoints, it is considered acceptable to have a relatively low power for this final endpoint in the testing sequence for the bimekizumab [REDACTED] treatment arm vs placebo

Table 9–1: Power calculation assumptions and methods

Endpoint	Power $\alpha = 0.025$, 2-sided		Assumptions		
	████	████	Week 16 Bimekizumab N=280 ^a	Week 16 Bimekizumab N=140	Week 16 Placebo N=70
HiSCR ₅₀	0.99	0.90	Proportion responders=0.60	Proportion responders=0.50	Proportion responders=0.25
HiSCR ₇₅	0.99	0.98	Proportion responders=0.45	Proportion responders=0.35	Proportion responders=0.10
Flare	0.99	0.99	Proportion of participants with flare by Week 16=0.09	Proportion of participants with flare by Week 16=0.19	Proportion of participants with flare by Week 16=0.52
DLQI	0.99	0.96	Mean CFB=-5.4; SD=6.8	Mean CFB=-4.8; SD=6.8	Mean CFB=-0.8; SD=6.6
Worst Pain CFB ^b	0.89	0.73	Mean CFB=-2.2; SD=3.2	Mean CFB=-2.0; SD=3.2	Mean CFB=-0.5; SD=3.7
Worst Pain Response ^c	0.95	0.53	Proportion responders=0.53	Proportion responders=0.43	Proportion responders=0.23

CFB=change from Baseline; ██████ SD=standard deviation

Note: Estimates for HS0004 are based on Week 12 data from the HS0001 study.

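### Pain response, the last alpha-controlled endpoint, is assigned to all randomised participants in Sections 3, 9.3.1 and 9.3.2 but powered only in those with Baseline pain at or above the threshold in Section 9.8

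*Protocol*

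**What the plan says.** Four places in the protocol bear on the population for pain response.

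- **Section 9.3.1** gives a general rule: "The primary and secondary efficacy analyses will be performed based on the RS". Section 9.1.2 defines that set: "The Randomized Set (RS) will consist of all randomized study participants".
- **Section 9.3.2, item 5** (and Section 3) defines the endpoint, assessed at Week 16, as "Pain response (defined as a decrease from Baseline in HSSDD weekly worst skin pain score at or beyond the threshold for clinically meaningful change", without a minimum Baseline score. On method it adds: "A similar analysis to the primary responder analysis will be performed".
- **Section 9.8** bases the power for the single-arm comparison on "the sample size of 104:52 in the subset of participants reporting Baseline HSSDD worst skin pain score at or beyond the threshold", and footnote c of Table 9-1 repeats the sizes 208, 104 and 52. The same section restates the endpoint without mentioning a decrease: "This additional endpoint is defined as HSSDD weekly worst skin pain score at or beyond the threshold for clinically meaningful change at Week 16".
- **Section 3** attaches a Baseline minimum to the non-confirmatory 30%-reduction pain endpoints, which are evaluated "among study participants with a score of" at least 3. The DLQI important-difference endpoint is likewise limited to a Baseline of at least 4.

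Section 9.8 describes pain response as the final endpoint in the testing sequence. Under Section 9.3.2, significance at that last step (Step 6) for one dose allows Steps 1 to 6 to be repeated at 0.05 for the other dose.

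**The concern.** A confirmatory endpoint needs one analysis population, and here the protocol supports two. Taken literally, Sections 3, 9.3.1 and 9.3.2 test everyone randomised. Section 9.8 plans for a subset and does not say that it departs from the RS rule. Because the authors write Baseline restrictions into other endpoints, their absence here cannot be put down to house style.

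The choice matters because a participant who starts below the threshold cannot improve by the threshold amount if the scale has a floor of zero. In the RS that participant is a non-responder whatever the treatment does. Response rates, odds ratio and power all depend on which population is used. The step also decides whether alpha passes to the other dose, so which test releases that alpha should not be open to choice at unblinding.

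**Working it through.** **Inputs.** From Section 9.8 and Table 9-1: Week 16 groups of 280 (pooled bimekizumab), 140 (single arm) and 70 (placebo); subset sizes 208, 104 and 52; responder rates 0.53, 0.43 and 0.23; two-sided alpha 0.025, or 0.05 if alpha is passed on; stated powers 0.95 (pooled, 0.025), 0.53 (single arm, 0.025) and 0.65 (single arm, 0.05). Assumption: the 11-point scale runs from 0 to 10. The value of the threshold is not needed.

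**Step 1: reproduce the stated power.** Fisher exact power, with each tail at alpha/2, is the sum of the binomial probabilities of all tables that reject.

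- 208 v 52, 0.53 v 0.23, alpha 0.025: 0.953 (stated 0.95)
- 104 v 52, 0.43 v 0.23, alpha 0.025: 0.538 (stated 0.53)
- 104 v 52, 0.43 v 0.23, alpha 0.05: 0.651 (stated 0.65)

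With the same rates in the full 280/140/70, Fisher gives 0.991, 0.703 and 0.793, which do not match. The printed figures therefore belong to the subset.

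**Step 2: share that cannot respond in the RS.** The eligible share is 208/280 = 104/140 = 52/70 = 0.743. The remainder is 1 − 0.743 = 0.257 in each group: 72 of 280, 36 of 140 and 18 of 70.

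**Step 3: rates in the RS.** Those below the threshold contribute no responders, so RS rate = 0.743 × subset rate:

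- pooled: 0.743 × 0.53 = 0.394
- single arm: 0.743 × 0.43 = 0.319
- placebo: 0.743 × 0.23 = 0.171

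The pooled odds ratio moves from (0.53/0.47)/(0.23/0.77) = 3.78 to (0.394/0.606)/(0.171/0.829) = 3.15.

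**Step 4: power in the RS, holding the method fixed.** The Wald columns use the log odds ratio, unadjusted for stratification, by exact enumeration. This is the type of test planned in Section 9.3.1.

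| Comparison | Stated | Fisher, subset | Fisher, RS | Wald, subset | Wald, RS |
|---|---|---|---|---|---|
| Pooled, 0.025 | 0.95 | 0.953 | 0.915 | 0.964 | 0.927 |
| Single arm, 0.025 | 0.53 | 0.538 | 0.478 | 0.586 | 0.513 |
| Single arm, 0.05 | 0.65 | 0.651 | 0.591 | 0.701 | 0.637 |

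Moving from the subset to the RS costs about 4 to 6 points by Fisher and 4 to 7 by Wald.

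**The case against.** The strongest reply is that the consequence is small and the intention is visible. Section 9.8 names the subset and its criterion, footnote c repeats it, and a fuller statement may stand in the SAP, which is not shown here. Under the planned Wald test in the RS, power is 0.927, 0.513 and 0.637, within about 2 points of the printed figures. Section 9.8 says the endpoint was added after randomisation was complete, with the sample size already driven by the Worst Pain change-from-Baseline endpoint. It also accepts relatively low power for the single-arm comparison at this last step.

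Most of this stands, and it rules out several stronger readings that a reader might infer.

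- **That the trial was sized on pain response or is now underpowered.** It was not sized on this endpoint. The pooled comparison keeps more than 0.90 power in either population.
- **That Step 6 becomes the weak gate.** Table 9-1 gives the pooled Worst Pain change-from-Baseline step 0.89, below the figure for pain response in either population.
- **That type I error is inflated.** Either population gives a valid test once it is fixed in advance. An all-RS comparison with built-in non-responders respects randomisation and merely dilutes the rates in every group.
- **That participants still in severe pain would count as responders.** The Section 9.8 sentence omits the decrease from Baseline, but the synopsis, Section 3 and Section 9.3.2 all state it. It is a faulty abbreviation, not a rival definition likely to be programmed.

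What the reply does not remove is the contradiction. This is not a detail left to the SAP: the protocol fixes the RS in one place and plans on a subset in another.

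**Conclusion.** The protocol gives pain response at Week 16 two incompatible analysis populations, and this should be reconciled. Followed as written, Sections 3, 9.3.1 and 9.3.2 would bring about 26% built-in non-responders into a confirmatory test. Planned rates would fall to 0.39/0.32/0.17, and power to about 0.92, 0.48 and 0.59 by the method that reproduces the stated 0.95, 0.53 and 0.65. The loss is modest and calls for no change in sample size. The larger matter is that the test at the end of the alpha-controlled sequence is not uniquely specified.

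The size rests on two assumptions: a scale with a floor of zero, and the planning split of 208/104/52. The share of randomised participants actually below the threshold is not in the document, so the 26% is a planning figure and not an observed one.

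Severity: should be fixed.

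**What to change.** Make one of two changes before unblinding.

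1. **Subset.** In Section 3 and Section 9.3.2 item 5, define pain response among randomised participants whose Baseline HSSDD weekly worst skin pain score is at or above the threshold. Name this in Section 9.3.1 as an exception to the RS rule, and keep the all-RS analysis as a sensitivity analysis. The present power figures then stand.
2. **Randomized Set.** Leave Sections 3, 9.3.1 and 9.3.2 as they are, and restate the responder rates and power for pain response in Section 9.8 and Table 9-1 for 280/140/70.

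Either resolves the conflict. In both cases, correct the Section 9.8 definition to a decrease from Baseline at or beyond the threshold.

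The cost is wording only, with no new data. The subset option limits the conclusion to participants with at least threshold-level pain at Baseline. The RS option accepts diluted rates and, by the same method, slightly lower stated power.

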A logistic regression model will be used to assess the effect of bimekizumab vs placebo on HiSCR₅₀ response. The model will include a fixed effect for treatment. The stratification variables of Hurley stage and prior antibiotic use will be added to the model unless inappropriate. The odds ratio versus placebo, p-value (from Wald test), and confidence interval will be calculated.

To assess the impact of the COVID-19 pandemic on the primary efficacy endpoint analysis, additional sensitivity analyses will be performed as specified in Section 9.3.4.

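### The Week 16 pain-response model leaves out Baseline worst pain, although the ANCOVA on the same score includes it: an efficiency gap of nil to about 8 power points for the N=140 comparison, not a validity error

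*Protocol*

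**What the plan says.** Protocol section 9.3.2, item 5, defines pain response by the decrease from Baseline in weekly worst skin pain on the HSSDD. Its wording is: "at or beyond the threshold for clinically meaningful change) at Week 16. A similar analysis to the primary responder analysis will be performed". The model is thus fixed by cross-reference to 9.3.1, which describes a logistic regression with a Wald test:

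- On the treatment term: "The model will include a fixed effect for treatment".
- On further covariates, it adds only this: "The stratification variables of Hurley stage and prior antibiotic use will be added to the model unless inappropriate".
- The summary measure is the "conditional odds ratio comparing bimekizumab to placebo adjusted for stratification factors used in the randomization".

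No Baseline score appears in that model. Item 4 of the same list, the change from Baseline in the same worst-pain item, is specified differently: "Analysis will be based on an ANCOVA with treatment and stratification variables as fixed effects and the Baseline values as covariate". Item 3 (DLQI) does the same.

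Pain response is Step 6, the last step for each dose. Section 9.8 explains that it was added after randomization was complete, on a sample size driven by the continuous pain endpoint. For the N=140 regimen, section 9.8 starts from those who reach the threshold before treatment: "With a 2-sided significance level of 0.025, the sample size of 104:52 in the subset of participants reporting Baseline HSSDD worst skin pain score". That number, it says, "provides 53% power for detecting a statistically significant difference between bimekizumab" and placebo. At the 0.05 level it gives 65%. Table 9-1 gives 0.95 for the pooled N=280 comparison. Section 9.8 states openly that the low power for the N=140 arm is accepted.

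**The concern.** A responder here is someone whose score falls by a fixed absolute amount on a bounded 11-point scale, and power is sized on participants whose Baseline is at or above that amount. A participant at the threshold must fall to zero to respond; one near the top of the scale can respond at several final scores. A link between Baseline pain and response is therefore plausible by construction. It is more direct than for HiSCR, which is built on a percentage reduction.

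The covariate costs nothing to obtain. The diary is completed daily from the start of Screening, and its Baseline value already enters item 4. The protocol names Baseline as a covariate where it wants one (items 3 and 4) and does not name it in item 5.

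At stake is some power at the lowest entry in Table 9-1. The sample size can no longer be raised there, so a prespecified prognostic covariate is one of the few levers left. Adjustment would also take account of chance differences in Baseline pain against a placebo group of about 52.

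**Working it through.** **Inputs from the protocol.** Response rates of 0.43 (N=140 regimen) and 0.23 (placebo) come from Table 9-1. The sample sizes, 104 and 52, and the two-sided levels, 0.025 and 0.05, come from section 9.8. For the pooled comparison the rates are 0.53 and 0.23, with 208 and 52.

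**Assumed, because the protocol does not give it.** The association between Baseline pain and response among participants at or above the threshold.

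**1. Reproducing the stated power.** The exact power of Fisher's test (one-sided p at most alpha/2) is 0.538 at 0.025 and 0.651 at 0.05 for 104:52, and 0.953 for 208:52. The protocol states 0.53, 0.65 and 0.95, so all three reproduce.

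**2. Power of the planned kind of test.** The plan analyses by logistic regression with a Wald test, not Fisher's test. A pooled two-proportion approximation gives a guide:

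- Mean rate = (104 × 0.43 + 52 × 0.23)/156 = 56.68/156 = 0.3633.
- SE under the null = √[0.3633 × 0.6367 × (1/104 + 1/52)] = 0.0817.
- SE under the alternative = √(0.43 × 0.57/104 + 0.23 × 0.77/52) = 0.0759.
- Power at 0.025 = Φ[(0.20 − 2.241 × 0.0817)/0.0759] = Φ(0.22) = 0.588.
- Power at 0.05 = Φ[(0.20 − 1.960 × 0.0817)/0.0759] = Φ(0.53) = 0.700.

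Simulated Wald logistic tests without Baseline agree: about 0.59 and 0.70. Any gain must be counted from these figures, not from 0.53 and 0.65.

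**3. A range for the assumption.** If Baseline and Week 16 scores have equal SDs and correlation r, change and Baseline correlate at √[(1 − r)/2]. That is 0.59 at r = 0.3, 0.50 at r = 0.5 and 0.39 at r = 0.7. Restricting to Baseline at or above the threshold lowers this to roughly 0.3 to 0.5. The range 0 to 0.5 also covers the case of no association.

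**4. Adding Baseline.** The simulation uses a latent-normal response correlated with Baseline, with marginal rates held at 0.43 and 0.23, n = 104:52, and the Wald test:

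| Assumed latent correlation | Power at 0.025 | Gain from 0.59 | Power at 0.05 | Gain from 0.70 |
|---|---|---|---|---|
| 0 | 0.59 | nil | 0.70 | nil |
| 0.2 | 0.60 | 1 point | not run | – |
| 0.3 | 0.615 | 2.5 points | 0.72 | 2 points |
| 0.4 | 0.64 | 5 points | 0.74 | 4 points |
| 0.5 | 0.67 | 8 points | 0.77 | 7 points |

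**5. Cross-checks at 0.025.**

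- With the association expressed as an odds ratio per Baseline SD, adjusted power is 0.58 at 1.0, 0.60 at 1.5, 0.63 at 2.0 and 0.66 at 2.5. At 3.0 it is 0.69, still below 0.70.
- A bounded 0–10 scale was also simulated, with an assumed threshold of 3 and Baseline restricted to at least 3. If the slope of follow-up on Baseline is 0.3, power moves from 0.584 to 0.645; at 0.5, from 0.587 to 0.624; at 0.7, from 0.559 to 0.571. At 0.9 and 1.0 nothing is gained.
- Adjustment did not lower power beyond simulation noise in any setting.

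**6. Two features of the plan that shrink the gain.**

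- Under the primary's composite strategy, antibiotic rescue or stopping for an AE or lack of efficacy counts as non-response. If that accounts for an assumed 15–25% of participants and is unrelated to Baseline pain, the gain at 0.025 is about 1–2 points at correlation 0.3, 3–4 at 0.4 and 5–7 at 0.5.
- Step 6 is reached only if the continuous pain test passes. The chance of passing both at 0.025 rises from about 0.55 to 0.56, 0.56 to 0.59 and 0.57 to 0.61 at full-population correlations of 0.3, 0.4 and 0.5.

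The simulations leave out the stratification factors and missing data.

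**The case against.** The best case for the plan has three parts. First, section 9 says the SAP will give more detail, and a similar analysis is not a closed list of covariates, so the SAP may already add Baseline pain. Second, the protocol follows one convention: every binary endpoint takes the primary model, and every continuous one takes ANCOVA with Baseline. Third, section 9.8 discloses the low power for the N=140 arm and accepts it, given the strength of the other comparison.

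Much of this stands. The wording leaves room for the covariate, the convention is coherent, and the sponsor has not hidden the low power. What remains is that the protocol does state a covariate set by cross-reference and names Baseline two items earlier for the same pattern of data. Accepting an inherited sample size is also no reason to pass over power that needs no new data.

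Some stronger readings are tempting but not supported:

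- **That the test is invalid or biased.** Randomization protects the type I error without the covariate, and chance imbalance is not bias.
- **That this is the weakest confirmatory test overall.** That is so only for the N=140 comparison. In the pooled comparison pain response has 0.95, and the lowest entry is the continuous pain change at 0.89.
- **That alpha passing between doses hinges on this.** Section 9.8 expects alpha to pass from the pooled comparison to the N=140 regimen, and that gate is already strong.
- **That power would rise from 0.53 to 0.67.** Those two figures come from different tests.
- **That the gain is about 15 points.** Scaling the variance by 1 − ρ² at ρ = 0.5 gives 0.59 to 0.74, but this shortcut overstates what the logistic test itself gains in simulation at the same correlation (about 8 points).

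**Conclusion.** The point holds as a small efficiency gap. As written, the confirmatory pain-response model omits a Baseline value that the trial collects and already uses for the continuous analysis of the same score. For the N=140 comparison, adding it raises the power of the Wald logistic test from about 0.59 by nil to about 8 points at 0.025, and from about 0.70 by nil to about 7 points at 0.05. These gains rest on assumed latent correlations of 0 to 0.5, which the protocol neither gives nor rules out, and on its rates of 0.43 and 0.23 at 104:52. They shrink under composite non-response unrelated to Baseline pain. The adjusted test would still be modestly powered. Little is to be gained in the pooled comparison. Optional, low severity.

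**What to change.** Before unblinding, state in section 9.3.2 item 5, and in the SAP, that pain response is analysed by logistic regression with treatment, the stratification variables and the Baseline HSSDD weekly worst skin pain score as a continuous covariate, in line with item 4. Keep the model without Baseline pain as a sensitivity analysis.

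The cost is one line of text and no new data. The one small drawback is interpretive: the odds ratio becomes conditional on Baseline pain as well as the stratification factors, so it is not directly comparable with the odds ratios for the other binary endpoints. A sentence in the SAP can say so. If the SAP already specifies this covariate, only the protocol wording needs to be aligned.
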